All products will be stored according to instructions from the manufacturer, in a dry and cool place at a temperature below 30° C out of direct sunlight. Prior to providing participants with products, the products will be inspected visually for damage. Quality control procedures will be detailed in a study standard operating procedure (SOP).

Outcomes

The outcomes of the study, their definitions, and type of analysis (non-inferiority or superiority) are listed in Table 3. Treatment outcomes will be evaluated through non-inferiority, and post-treatment outcomes will be evaluated through superiority analyses. This is because the intervention products may have the important benefits described above of being lower cost than the standard RUTF, increased potential to be produced locally, and free of aflatoxin, but evidence is needed to confirm they are acceptably similar in treatment outcomes. The composition of these alternative formulations may also improve gut health, possibly reducing the risk of relapse. Thus, post-discharge relapse outcomes are analyzed in superiority analyses.

Table 3. Primary and secondary study outcomes

Outcomes	Definition	Type of analysis
Primary outcomes		
Anthropometric recovery at discharge	WLZ \geq -2 and MUAC \geq 125 mm and absence of bilateral pitting edema for two consecutive visits	Non-inferiority
Relapse to wasting within 3-months post-discharge	A new episode of wasting (defined as WLZ/WHZ $<$ -2 or MUAC $<$ 125 mm or presence of bilateral pitting edema) within the 3-month period following recovery from the index wasting episode, among children who recovered from their index episode	Superiority
Secondary outcomes		
Length of stay (LOS) among recovered children:	The number of days between the day the child is admitted to treatment and the day the child is determined to be recovered and thus discharged from treatment	Non-inferiority
Weight gain	Change in child's weight (gram/kilogram/day) between weight on day of admission to treatment and day of discharge	Non-inferiority
Default from treatment	Child is absent for two consecutive visits, declared a defaulter on the second visit	Non-inferiority
Transfer to inpatient treatment	Referral or admission to hospital for inpatient treatment during the treatment course	Non-inferiority

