## Background

Acute malnutrition is the most life-threatening form of undernutrition. Moderate and severe acute malnutrition (MAM, SAM) are effectively treated with ready-to-use therapeutic foods (RUTFs) but there is a need to lower the cost of treatment and improve treatment regimens to reduce risk of relapse MAM/SAM episodes following recovery. The currently used standard formulation of RUTF contains peanuts and dairy, which pose problems due to their high cost, the need to import ingredients to the Global South (in the case of dairy), and risk of aflatoxin (in the case of peanuts). Before alternative formulations of RUTF can be recommended, however, there is the need for data on the non-inferiority of these formulations compared to the most commonly used milk- and peanut based RUTF on recovery rates and to what extent recovery is sustainable. Sustainable recovery implies a lower rate of post-treatment relapse. In this study we evaluate two novel RUTF formulations, one that is peanut and milk-free based on soy, maize and sorghum (SMS-RUTF) and one with reduced milk based on soy (S-RUTF).

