### Study design

#### Main trial

This will be a facility-based, triple blinded individually randomized controlled trial with three arms, including two interventions and one control arm, with a 1:1:1 allocation ratio. Children will be enrolled upon initiation of MAM or SAM treatment and followed monthly for 3 months post-discharge from treatment.

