## Study outcomes

### Main trial

The primary and secondary outcomes for the main trial and their definitions are listed in Table 1. Outcomes are the same for MAM and SAM children.

*Table 1. Primary and secondary efficacy outcomes*

Outcomes	Definition	Type of analysis
Primary outcomes		
Anthropometric recovery at discharge	WLZ $\geq$ -2 and MUAC $\geq$ 125 mm and absence of bilateral pitting edema for two consecutive visits, at the day of end of treatment	Non-inferiority
Relapse to wasting within 3 months post-discharge	A new episode of wasting (defined as WLZ/WHZ $<$ -2 or MUAC $<$ 125 mm or presence of bilateral pitting edema) within the 3-month period following recovery from the index wasting episode, among children who recovered from their index episode	Superiority
Length of stay (LOS) among recovered children	The number of days between the day the child is admitted to treatment and the day the child is determined to be recovered and thus discharged from treatment	Non-inferiority
Weight gain	Change in child's weight (gram/kilogram/day) between weight on day of admission to treatment and the day of end of treatment	Non-inferiority
Anthropometry at discharge from treatment	WLZ/WHZ, MUAC, weight, height/length, LAZ/HAZ and WAZ at the day of end of treatment	Non-inferiority
Anthropometry at 3-months post-discharge	WLZ/WHZ, MUAC, weight, height/length, LAZ/HAZ and WAZ at 3-months post-discharge (3 months after the day of end of treatment)	Superiority
Hemoglobin at discharge	Hemoglobin concentration (grams/liter) at the day of end of treatment	Non-inferiority
Hemoglobin at 3-months post-discharge	Hemoglobin concentration (grams/liter) at 3-months post-discharge (3 months after the day of end of treatment)	Superiority
Secondary outcomes		
Default from treatment	Child is absent for two consecutive visits, declared a defaulter on the second visit	Non-inferiority

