### Sample size and statistical power

#### Main trial

We estimate a total sample size of 1080 children with SAM (360 per arm) and 1080 children with MAM (360 per arm) will provide sufficient statistical power to demonstrate non-inferiority for each comparison, with a non-inferiority margin of relative 12.5%, assuming a recovery rate in the control of 76% and a loss to follow up of 15% (Table 4). The sample size will be smaller for analyses of relapse, because only recovered children will be included in the analysis. All calculations assume a one-sided  $\alpha = 0.05$  for non-inferiority and two-sided  $\alpha = 0.05$  for superiority analyses,  $\beta = 0.8$ , and 15% attrition. While the key objectives of this research are to evaluate effects of the alternative RUTFs on recovery and relapse, we consider as primary outcomes any outcome for which we have adequate power for clinically or policy meaningful effect sizes (5).

 Stata commands `ssi` for continuous outcomes and `artbin` for binary outcomes were used for non-inferiority analyses, and `power twomeans` for continuous outcomes and `power twoproportions` for binary outcomes were used for superiority analyses. Outcome proportions, means, or standard deviations were taken from relevant studies in literature as delineated in Table 4.

Table 4. Calculations of detectable effect sizes for all outcomes

Outcome	Outcome prevalence in the literature	Type of analysis	Non-inferiority margin (relative) with $\geq 80\%$ power (Non-inferiority)	Detectable effect size at 80% power (Superiority)	Rank of outcome
Anthropometric recovery at discharge	MAM recovery (with RUSF*): 73% (6); 73% (7); 85% (8)  SAM recovery: 55.4% (9); 82.3% (10); 76% (11); 71% (pooled estimate from meta-analysis) (12)	Non-inferiority	12.5% relative margin		Primary
Relapse to wasting within 3-months post-discharge	Post-MAM relapse: 30% within 3 months (13); 33% within 12-months (14)  Post-SAM relapse: 6.8% 3-month cumulative incidence (15); 24% 2-month cumulative incidence (16); 30% within 3-months (unpublished)	Superiority		Risk difference of 11%; Relative risk = 0.72	Primary
Length of stay (LOS) among recovered children	MAM: 36.4 days (SD 50.4 days)(17); 5.9 weeks (95% CI: 4.9, 7.0)(18) SAM: 56 days (assumed 41 day SD) (9)	Non-inferiority	MAM: 4.9 days; 12.5% relative margin SAM: 8 days; 12.5% relative margin		Primary

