### Study accrual

We will report the numbers of participants who were randomized, received intended treatment, and were included in the analyses for primary outcomes. These numbers will be presented in the format as depicted in Figure 1 consistent with the flow diagram required for CONSORT reporting.

Figure 1. Study accrual profile for the main trial

\*Children will be included in analyses of relapse outcomes if they recovered and had at least one post-discharge visit

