## Analysis frame

Our primary analysis frame will be intention-to-treat (ITT). ITT groups will be defined by the randomization assignment to which participants are allocated; that is, all participants will be included in the analysis based on the treatment group to which they were randomized.

However, ITT analyses can bias effect sizes toward the null, spuriously demonstrating non-inferiority, because non-compliance diminishes any treatment effects (30). Despite this, ITT is still the recommended approach for non-inferiority trials (31). To mitigate this concern, we will conduct a secondary analysis in which we repeat all analyses with a Complier Average Causal Effects (CACE) approach. CACE analyses adjust for any differences between children who adhere vs do not adhere in characteristics that may influence outcomes, thus mitigating concerns of confounding. CACE analyses are also useful for superiority analyses, as these results can distinguish between the effects of the interventions themselves, and effects of the adherence to the interventions. Both ITT and CACE results will be presented. This is summarized in Table 5.

Adherence will be defined as attendance at all treatment visits. The characteristics to be considered for adjustment and the decision rules to determine whether adjustment will be made will be the same as described in the next section below.

*Table 5. Analysis approaches and sensitivity analyses by type*

Analysis type	Primary analysis	Secondary analysis	Sensitivity analyses
Non-inferiority	ITT	CACE	Exclusion of children who received both study products and standard of care products during treatment course
Superiority	ITT	CACE	Exclusion of children who received both study products and standard of care products during treatment course

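### Relapse and length of stay are compared only in children who recovered, a group formed after randomisation, and no supportive endpoint counts children recovered and relapse-free among all randomised

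*SAP*

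**What the plan says.** SAP Table 1 (Study outcomes, Main trial) restricts the relapse outcome to events "within the 3-month period following recovery from the index wasting episode, among children who recovered from their index episode". Protocol Table 3 has the same limit: "among children who recovered from their index episode". The footnote to SAP Figure 1 (Study accrual) adds a second condition that arises after randomisation: "Children will be included in analyses of relapse outcomes if they recovered and had at least one post-discharge visit". SAP Table 1 also lists as primary "Length of stay (LOS) among recovered children".

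The SAP's only comment on the restriction concerns numbers: "The sample size will be smaller for analyses of relapse, because only recovered children will be included in the analysis". Its Analysis frame section describes the primary frame as intention-to-treat, in which "all participants will be included in the analysis based on the treatment group to which they were randomized".

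Neither of the other planned analyses deals with selection on recovery. The CACE analysis concerns attendance at visits. The single sensitivity analysis concerns children switched to the standard product near expiry. SAP Statistical methods makes no multiplicity adjustment and does not make the relapse test depend on the recovery result.

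The Background frames the need as recovery rates and "to what extent recovery is sustainable. Sustainable recovery implies a lower rate of post-treatment relapse". Objective 2 is relapse after recovery.

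**The concern.** Recovery is affected by treatment, so the recovered children in two arms need not be comparable. If one product recovers fewer children and the ones it misses are the more fragile, they leave its relapse denominator and its relapse rate falls without any benefit. Length of stay is open to the same effect: a slow recoverer who passes the 12-week limit drops out of the mean instead of lengthening it.

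A relapse claim has consequences. Under SAP Sub-study 3 (Costing), superiority on relapse is enough to start the cost-per-DALY model, whose stated effects include those on relapse. An apparent gain produced by fewer recoveries could therefore be carried into that model as health benefit.

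**Working it through.** **The plan's own figure.** Protocol Table 4 has 306 children per arm per stratum after 15% attrition (360 × 0.85) and 77% recovery: 306 × 0.77 = 235.6, so 236 in the relapse analysis. Two proportions, 30% vs 20%, two-sided 0.05, pooled variance: power 71.0%, as stated.

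**Inputs for the illustration.**
- Control recovery 76% (SAP, Sample size and statistical power).
- Control relapse 30% (Protocol Table 4).
- 306 analysed per arm.
- Product recovery 68%: assumed; RR 0.68/0.76 = 0.895, against a margin of 1 − 0.125 = 0.875.
- No effect of the product on any child's relapse, and every child it recovers would also recover on control: assumed.
- q, the relapse risk that the 8% it fails to recover would have had: not in the documents; assumed 40–60%.

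**Formulas.** Sustained recovery is recovery × (1 − relapse).
- Control: 0.76 × 0.70 = 53.2%.
- Product relapse among recovered: (0.76 × 0.30 − 0.08q)/0.68.

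The last two columns are simulated with log-RR Wald intervals: non-inferiority one-sided 95% against 0.875, relapse two-sided 95%. Superior relapse is read as an interval wholly below 1.

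| q | Relapse, product | RR | Sustained recovery, product | Falsely lower relapse | Same, and recovery non-inferior |
|---|---|---|---|---|---|
| 40% | 28.8% | 0.96 | 48.4% | about 4% | about 0.5% |
| 50% | 27.6% | 0.92 | 49.2% | about 8% | about 0.9% |
| 60% | 26.5% | 0.88 | 50.0% | about 12% | about 1.5% |

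Reference points:
- With identical products (76% in both arms), false relapse superiority occurs about 2.4% of the time, and about 2.2% jointly with non-inferior recovery.
- At q = 30% the relapse RR is 1.00 and there is no bias.
- At q = 100% the joint probability is about 5.9%.
- A product with true recovery of 68% passes recovery non-inferiority only about 12% of the time.

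**Bound when recovery passes.** With control at 76%, observed recovery must be at least about 72.0%. Taking that as the true rate with q = 100%: (0.228 − 0.040)/0.720 = 26.1%, RR 0.87. Across the cases tried at 77% control recovery, the joint probability did not exceed about 8% (true recovery 72.5%, q = 100%).

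**Length of stay.** Assume log-normal recovery times with 76% and 68% recovered by day 84.
- Log-SD 0.5: the means among recovered are 51.2 and 54.0 days, a difference of 2.8. Restricted means to day 84 are 0.76 × 51.2 + 0.24 × 84 = 59.1 and 0.68 × 54.0 + 0.32 × 84 = 63.6, a difference of 4.5.
- Log-SD 0.9: the differences are 3.3 and 6.0 days.

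Under this assumption the recovered-only comparison shows about 55–62% of the delay seen in all children (3.3/6.0 and 2.8/4.5).

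**Power of a composite.** If recovery is 77% in both arms and relapse 30% vs 20%, sustained recovery is 0.77 × 0.70 = 53.9% vs 0.77 × 0.80 = 61.6%. With 306 per arm the power is 48.7%; 80% would need 645 analysed per arm per stratum.

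**The case against.** The best reply is that the conditional question is the one the trial poses. The Background links sustainable recovery to a lower relapse rate, and Objective 2 concerns relapse after recovery. A reader might infer that sustained recovery is never tested; the documents do not support that, because it is tested in the sense they give it.

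A reader might also infer that the planned analyses would hide a recovery deficit. They would not. Recovery is primary in the same strata and comparisons, and non-response and default are secondary outcomes. Three-month anthropometry is a primary outcome not defined on recovery. That last safeguard is uncertain, however: Protocol Study procedures starts post-discharge visits once discharge criteria are met, while its Early withdrawal section intends to follow everyone.

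A third tempting reading is that the 12.5% margin lets recovery differ by that much unnoticed. The confidence bound, not the point estimate, must clear the margin. In the illustration a double success is less likely than with identical products.

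Finally, the direction and size depend on q, for which the documents give no figure.

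All of this stands. It limits the consequence but leaves the structural gap: the relapse contrast is not a comparison of randomised groups, the plan treats the restriction only as lost sample size, and nothing requires relapse to be read with recovery.

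**Conclusion.** The concern holds in limited form. Relapse and length of stay are compared in a group selected after randomisation, and no endpoint counts children recovered and still relapse-free among all randomised.

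In the illustration, the false-superiority rate for relapse rises from about 2.5% to about 4–12%, while sustained recovery is 3.2 to 4.8 points lower (53.2% vs 50.0–48.4%). This rests on an assumed 8-point recovery deficit and an assumed above-average relapse risk in the unrecovered children. Most of those false findings would sit beside a recovery result that did not show non-inferiority. The risk is therefore mainly that the relapse result is read, or passed to the cost model, on its own. The length-of-stay figures rest on an assumed distribution and show direction more than size.

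**What to change.** Keep the recovered-only analyses as planned and add to the SAP:

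1. A prespecified supportive analysis, for each stratum and each comparison with control, of recovered and relapse-free through 3 months among all randomised children, using the same regression. Unrecovered children count as failures. State how recovered children without a post-discharge visit are classified; the SAP plans no imputation, so this rule must be written down.
2. A sentence saying that relapse results will be reported and interpreted together with recovery and this composite.
3. For length of stay, a supportive restricted mean time to recovery to 12 weeks in all randomised children.

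The cost is SAP text and a few extra models, with no new data collection. The composite has only about 49% power for the planned relapse effect, so it should be supportive, not a replacement for relapse or a formal gate on it.

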## Study interventions

Children admitted into MAM or SAM treatment at the study centers will be randomized to one of three RUTF formulations:

- **Standard of care RUTF (control):** composed of milk powder, sugar, vegetable oil, peanut butter, vitamins, and minerals and low in fiber (~0.75g per 100g)
- **SMS-RUTF (intervention 1):** a milk- and peanut-free product with added crystalline amino acids that provide significantly more fiber (~5.0g per 100g)
- **S-RUTF (intervention 2):** a reduced-milk product

Burkina Faso national guidelines for MAM and SAM ambulatory treatment will be followed for dosing the products and all other aspects of treatment (4). Thus, all children will receive the standard of care for Community Management of Acute Malnutrition (CMAM) treatment in Burkina Faso, with the only difference between treatment arms being the product received. Burkina Faso national guidelines for CMAM are detailed in the guideline document (4). Briefly, upon admission to treatment for SAM, children will undergo medical evaluation and appetite test and receive routine antibiotics and rapid diagnostic test for malaria as well as other treatments as indicated in the guidelines. Caregivers of eligible children will be provided with RUTF and instructed on how to use it. Children will be followed weekly at the health center to be re-evaluated. At the follow-up visits, children's anthropometry will be measured, a clinical examination will be performed, and the caregiver will be provided with another 7-days' supply of RUTF with instructions. Children will be treated for a maximum of 12 weeks and will be eligible to be discharged when they have achieved anthropometric recovery (see definition below). For MAM, upon admission to treatment, children will be provided with RUTF to be used as a food supplement in addition to the child's usual diet. Caregivers will be provided with the product and instructed on its use and receive nutritional counseling as per guidelines. Children will receive medical treatments as indicated in the guidelines and instructed to return to the health facility every two weeks for monitoring. Children will be treated for a maximum of 12 weeks and be eligible for discharge when they have achieved anthropometric recovery.

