Weight gain during treatment	MAM: 4.1 g/kg/day (SD = 3.0) (17), SAM: 3 g/kg/day (SD = 4.7) in 6-23 mo and 8.6 g/kg/day (SD = 4.7) in 24-59 mo (19)	Non-inferiority	MAM: 0.14 kg; 12.5% relative margin SAM: 0.91 g/kg/day; 12.5% relative margin		Primary
Anthropometry at discharge from treatment	MAM: All estimates from Fabiansen et al (20) WLZ: -1.52	Non-inferiority	MAM:		Primary

	
MUAC: 130.1 mm HAZ: -1.86 WAZ: -2.6 (assumed from SAM because estimates not available) Weight: 7.8 kg Height: 72.9 cm
 
SAM: All estimates from Kangas et al(9) WLZ: -1.9 MUAC: 125.9 mm HAZ: -2.3 WAZ: -2.6 Weight: 7.3 kg Height: 71.6 cm
		
WLZ: 0.2 z-scores; 12.5% relative margin MUAC: 6.8 mm; 5% relative margin HAZ: 0.2 z-scores; 12.5% relative margin WAZ: 0.4 z-scores; 12.5% relative margin Weight: 0.4 kg; 5% relative margin Height: 3.8 cm; 5% relative margin
 
SAM: WLZ: 0.3 z-scores; 12.5% relative margin MUAC: 6.3 mm; 5% relative margin HAZ: 0.3 z-scores; 12.5% relative margin WAZ: 0.4 z-scores; 12.5% relative margin Weight: 0.4 kg; 5% relative margin Height: 3.8 cm; 5% relative margin
		
Anthropometry at 3-months post-discharge	MAM: All estimates from Fabiansen et al (20)	Superiority		MAM: WLZ: 0.26	Primary

	WLZ: -1.52 MUAC: 130.1 cm HAZ: -1.86 WAZ: -2.6 (assumed from SAM because estimates not available) Weight: 7.8 kg Height: 72.9 cm  SAM: All estimates from Kangas et al(9) WLZ: -1.9 MUAC: 125.9 cm HAZ: -2.3 WAZ: -2.6 Weight: 7.3 kg Height: 71.6 cm			MUAC: 2.46 cm HAZ: 0.39 WAZ: 0.37 Weight: 0.39 kg Height: 1.87 cm  SAM: WLZ: 0.37 MUAC: 3.13 cm HAZ: 0.48 WAZ: 0.37 Weight: 0.55 kg Height: 2.76 cm	
Hemoglobin at discharge	MAM: 108 g/L (SD = 13) (21) SAM: 108.6 g/L (SD = 11.2) (22)	Non-inferiority	MAM: 2.7 g/L; 2.5% relative margin SAM: 2.2 g/L; 2.5% relative margin		Primary
Hemoglobin at 3-months post-discharge	MAM: 108.0 g/L (SD = 13) (21) SAM: 108.6 g/L (SD = 11.2) (22)	Superiority	--	MAM = 2.9 g/L SAM = 2.9 g/L	Primary
Default from treatment	MAM: 6.8% (17) SAM: 8.5% (9)	Non-inferiority	MAM: 50% relative margin SAM: 45% relative margin		Secondary
Transfer to inpatient treatment	MAM: 5.8% (20) SAM: 20.1% (9)	Non-inferiority	MAM: 70% relative margin SAM: 40% relative margin		Secondary
Non-response to treatment	MAM: 32.2% (18), 28%(20) SAM: 12.5% (9)	Non-inferiority	MAM: 30% relative margin SAM: 25% relative margin		Secondary

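### Discharge-day MUAC and height are primary non-inferiority outcomes in the SAP, but their 5% relative margins cannot tell a clearly worse product from an equal one

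*SAP*

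**What the plan says.** SAP Table 1 lists anthropometry at discharge among the primary outcomes, type non-inferiority, and defines it as "WLZ/WHZ, MUAC, weight, height/length, LAZ/HAZ and WAZ at the day of end of treatment". Protocol Table 3 has the same outcome as secondary. The SAP section on sample size explains the rank: any outcome with adequate power for a clinically or policy meaningful effect is treated as primary.

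The day of measurement follows from the course of treatment. For SAM, "Children will be treated for a maximum of 12 weeks and will be eligible to be discharged when they have achieved anthropometric recovery"; the rule for MAM is equivalent. Recovery is WLZ at least -2 and MUAC at least 125 mm, with "absence of bilateral pitting edema for two consecutive visits, at the day of end of treatment". SAM visits are weekly; MAM caregivers are "instructed to return to the health facility every two weeks for monitoring".

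SAP Table 4 gives the SAM MUAC margin as "MUAC: 6.3 mm; 5% relative margin" and the MAM margin as 6.8 mm, also 5%. Height has 3.8 cm (5%) in both strata. The assumed discharge means are 125.9 mm and 71.6 cm (SAM) and 130.1 mm and 72.9 cm (MAM). The recovery margin is a relative 12.5%, "assuming a recovery rate in the control of 76% and a loss to follow up of 15" per cent. No adjustment is made for multiple comparisons.

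**The concern.** Two features weaken these tests.

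The first is the margin. A relative margin suits an outcome that can fall toward zero. MUAC and height cannot: a child enters the trial with most of the discharge value already present, and treatment adds only the last part. Five per cent of the level can therefore be a large share of everything the product is meant to achieve.

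The second is the day of measurement. A child who recovers is measured when WLZ and MUAC have met the thresholds at two visits. A slower product then tends to lengthen stay or reduce recovery, while the discharge values of the children who do recover stay near the thresholds. Height has a related problem: children kept longer are older when measured, which favours the slower product.

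At stake is the reading of the results. With primary rank, a pass on MUAC or height would be reported as a primary non-inferiority finding and then tested for superiority. It could stand beside a failed recovery test and appear to contradict it, although it carries almost no information about the product.

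**Working it through.** **1. The plan's margins.** Two conversions of a 5% relative margin are possible: 0.05 × mean, or mean/0.95 - mean.
- SAM MUAC: 0.05 × 125.9 = 6.3 mm (the other form gives 6.6).
- MAM MUAC: 130.1/0.95 - 130.1 = 6.8 mm (the other form gives 6.5).
- Height: 71.6/0.95 - 71.6 = 3.8 cm and 72.9/0.95 - 72.9 = 3.8 cm.

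All four reproduce, though not under one rule.

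**2. What the MUAC margin tolerates.** 125.9 - 6.3 = 119.6 mm (SAM) and 130.1 - 6.8 = 123.3 mm (MAM). Both lie below 125 mm, so an arm whose average child had not met the discharge criterion could be called non-inferior. If SAM children are admitted at 110-115 mm (assumption), the gain to 125.9 mm is 10.9-15.9 mm, and 6.3 mm is 40-58% of it.

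**3. Standard deviations.** The SAP gives none for these outcomes. I back-calculated them from the differences detectable at 80% power in Table 4 (3 months post-discharge): SD = d / (2.80 × √(2/n)). I took n = 306 (360 less 15%) or 233 (76% of 306), and read the MUAC differences, printed in cm, as mm.

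| | d | SD | SE of difference, n = 306 |
|---|---|---|---|
| SAM MUAC | 3.13 mm | 12.1-13.8 | 0.98-1.12 |
| MAM MUAC | 2.46 mm | 9.5-10.9 | 0.77-0.88 |
| SAM height | 2.76 cm | 10.6-12.2 | 0.86-0.99 |
| MAM height | 1.87 cm | 7.2-8.3 | 0.58-0.67 |

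**4. Chance of passing.** The Statistical methods section gives a non-inferiority rule only for the relative risk. I assume that a continuous outcome passes when the one-sided 95% bound of the difference lies inside the margin: P = Φ((margin - true difference)/SE - 1.645). At true equality, P is 100% for MUAC in both strata, 99-100% for SAM height and 100% for MAM height.

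**5. A product that fails on recovery.** 0.67/0.77 = 0.870, below 0.875. With a 10-15 mm MUAC gap between recovered and non-recovered children (assumption), the mean difference is 0.10 × 10 to 0.10 × 15 = 1.0-1.5 mm. The worst SAM case is (6.3 - 1.5)/1.117 - 1.645 = 2.65, so P = 99.6%. MAM is 100%.

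For the expected MUAC difference to equal the SAM margin, recovery would have to fall by 6.3/15 to 6.3/10 = 42-63 percentage points. The recovery margin is 0.125 × 76 = 9.5 points.

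**6. Height.** The true difference at which the test passes half the time is 3.8 - 1.645 × SE: 2.2-2.4 cm (SAM) and 2.7-2.8 cm (MAM). If growth in height stopped completely on a new product, the SAM test would still pass more often than not unless control children gained more than about 2.2-2.4 cm during treatment. Over the SAM stay of 56 days in Table 4, that is 2.18/8 to 2.39/8 = 0.27-0.30 cm a week. The documents state no expected height gain.

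**7. Simulation of the discharge rule.** This has two consecutive qualifying visits or a stop at 12 weeks, with control recovery set to 76%. Admission values, two spreads of gain rate (log-SD 0.4 and 0.8), and 8 mm (SAM) or 6 mm (MAM) of MUAC per WLZ unit are assumptions. All children are analysed. Results for gain 30% slower:

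| | Recovery | MUAC passes | WLZ passes | MUAC at fixed week 4 | WLZ at fixed week 4 |
|---|---|---|---|---|---|
| SAM | 48-61% | 100% | 3-4% | 87-100% | 0-8% |
| MAM | 58-64% | 100% | 2-7% | 100% | 3-50% |

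The simulated MUAC spread is narrower than the SAP implies (MAM end-of-treatment SD 2.8-4.5 mm against 9.5-10.9 mm), so I rechecked SAM. In the wider-spread run the mean MUAC difference was 2.52 mm. With the SDs in step 3, that passes 96-99% of the time.

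If only recovered children had an end-of-treatment value, WLZ would pass 53-87% (SAM) and 9-30% (MAM) at the same slowing.

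**The case against.** A reader might infer that non-inferiority is close to guaranteed for all six anthropometry measures, whatever the product does. The documents do not support that.

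- The discharge rule uses only WLZ, MUAC and edema. Height and LAZ/HAZ are not criteria; weight and WAZ are tied to it only indirectly.
- Children are not measured on the day they first cross the thresholds. Recovery must hold at two visits, so discharge comes at least 7 days (SAM) or 14 days (MAM) later. The intention-to-treat analysis also includes children who did not recover.
- WLZ can fail. It almost always does once gain is 30% slower, if all children are measured. On the implied SDs, power at equality is only 70-83% for WLZ, 42-64% for HAZ and 65-76% for SAM weight.
- Even SAM MUAC fails if the product is bad enough: in the simulation it never passed with gain 75% slower.

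All of this stands, and it confines the point to MUAC and height.

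It can also be said that recovery, length of stay and weight gain are separate primary outcomes that would expose a slower product, and that nothing lets discharge anthropometry override a failed recovery test. That limits the harm. It does not justify primary rank for a test that adds no discrimination.

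Finally, one might blame timing and simply move the measurement to week 4. The simulation argues against this: with the margin unchanged, MUAC still passes 87-100% of the time, and the MAM WLZ test can become less sensitive.

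**Conclusion.** The concern holds for MUAC and height. Their 5% margins are the main cause. For MUAC the outcome-dependent measurement day adds to it; for height the day can favour the slower product.

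The limits of 119.6 and 123.3 mm follow from SAP figures alone. The pass probabilities at equality use SDs implied by Table 4 and the assumed decision rule. The 1.0-1.5 mm difference rests on the assumed 10-15 mm gap, and the simulation on assumed admission values and gain rates. The height result is conditional on actual height gain, which the sponsor can check in its own data.

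WLZ is attenuated, not neutralised. The attenuation is larger if children who default or transfer have no end-of-treatment value. The SAP does not say what value they receive, and it rules out imputation.

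**What to change.** 1. Do not declare primary non-inferiority on discharge-day MUAC and height. Report them descriptively, or as secondary in line with protocol Table 3.
2. If a growth test is wanted beyond the existing weight-gain outcome, test change from admission at a fixed time from randomisation. Use the scheduled visits and the admission value as covariate. Set the margin as a fraction of expected gain, not of the level, and justify it.
3. State the decision rule for continuous non-inferiority outcomes, and what value is used for children who default or transfer.

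The cost is SAP wording and analysis of measurements already scheduled; no new data are needed. The price is fewer primary non-inferiority claims. A gain-based margin will be tighter and its power lower, and that power must be stated. Children discharged before the fixed day would contribute their earlier visits through a mixed model.
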